### **3.3 Study Design**

This is a quasi-experimental(QED), longitudinal design study to collect data on the effectiveness of a kangaroo care education programme (KC-EP) for mothers', nurses' and infants' outcomes. The QED is often described as a non-randomized, pre-post intervention study that is common in healthcare research when it is not logistically practicable or ethical to carry out a randomized control trial (Levin & Kate, 2007). This study met all four criteria of Harris, McGregor, Perencevich, Furuno, Zhu, Peterson, & Finkelstein (2006). Each reason is discussed below. In a human study, randomization in the intervention of known efficacy would not be allowed, unless the effectiveness is not known or doubtful. According to Jotzo, Martina & Christian (2005), psychological and mental support is required in critical circumstances, i.e. after premature birth. In the emotionally sensitive NICU environment, it seems unethical to provide some mothers with help, but other people oppose randomization for other reasons. A QED is an empirical instrument used to measure the causal effect of an

intervention on the basis of longitudinal evidence to decide whether the intervention has led to improvements in the outcomes of the target population. This study evaluated the effect of an educational programme on the outcomes of mothers, nurses, and preterm infants regarding KC techniques.

A QED design is considered an adequate technique for evaluating the causal and successful relationship between the independent and dependent variables found when a fully experimental or randomized control trial (RCT) design is not feasible (Harris et al., 2006). RCT is also not realistic for research into small-scale continuing education. Due to the aspect of non-random assignment to the control group or experimental group, a quasi-experimental research design was chosen as a multilevel intervention for the preterm infant. The experimental group participated in a structured training programme on evidence-based experience and skills: a KC-EP for mothers and nurses. The mother-infants dyad in the control group followed the standard unit practice, and both groups had homogeneous or similar characteristics.

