### 3.16.1 Data Collection Method for Mothers in the Control Group

Based on the day of the preterm infant's admission to the NICU, the researcher screened and recruited its mother into the control group. The mothers and premature infants were medically and surgically stable. The researchers chose mothers who were ready and returned after 48 hours to meet those who were interested to participate in the study. The selection was determined according to the mother's and premature infant's condition (clinically stable and eligible to perform KC), while the length of gestation had to be between 28 to 36/6 weeks. The study samples were selected from early February 2018 to the end of July 2018, within six months of the mothers in the control group. An average of two to four mothers was recruited per week. Mothers had to fill out a consent form. Consent was obtained from all mothers before they were recruited. The researchers contacted the participants in order to give an explanation of what was involved.

Questionnaire I for mothers was provided in an English and bahasa Melayu version. All mothers were given the same questionnaire in three phases ; T0, T1, and T2. At T0, all mothers were given the questionnaire on a voluntary basis to determine their perspectives on the implementation of KC as a baseline. The researchers created an identification code number for each of the mothers to be placed on the envelopes. Thus, mothers' answers could be matched for the T0, T1, and T2 questionnaires. The identification code started from MCG01 (mother control group 01). After a welcome speech and briefing (10 to 15 minutes), the questionnaires were given to the mothers to fill in and then collected. The mothers in the control group were also given a Kangaroo Care Progress Record (KCPR) booklet to record weight gain, feeding status, the routine practice of KC in the clinical setting and after discharge until 3 months old but without any information or input related to KC.

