The control group mothers came for visits and saw their preterm infants once a day for 30 minutes to 1 hour, and exercised KC if they were interested. This was the NICU's routine practice. The control group of mothers continued routine ward practice and standard hospital care. Mothers who declined to participate during the time of the study were excluded. For participation in the study, a small token gift was given to (n=48) mother-infant dyads at the control group.

Upon their premature infant's discharge from the hospital, the mothers were reminded to answer the same standardized questionnaire (QI) for T0, T1, and T2. The following posttest questionnaires (Questionnaire I: enclosed in the envelope) were given to the mothers at the NICU or the Pediatrics Clinic on the 1st and 3rd month, when they came for their premature infant's follow-up, and were returned the same day. Consequently, some of the data were collected and sent by email if the mothers could not keep to the time (received on the same day).

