### **3.16.2 Data Collection Method for Mothers in the Experimental Group**

The recruitment of the experimental group of mothers was based on premature infant's day of admission to the NICU after data collection from the nurses was completed. This was done to keep mothers in the experimental group from being exposed to the control group during their hospital stay. Both mothers and premature infants were medically and surgically stable, and mothers were willing to perform KC. For the experimental group of mothers, data collection was carried out over seven months from early October 2018 to the end of April 2019, after the nursing intervention program for nurses (KC-EP) had been completed. An average of two to four mothers was recruited per week.

The mother-infant dyads were recruited within 48 hours, as soon as they were clinically stable and eligible to perform KC. Samples were selected by the researcher, who returned after 48 hours to meet mothers interested in the study and agreed to complete the consent form. Prior to recruitment, consent was sought on a voluntary basis from all (n=48) mothers (Appendix B). The researchers explained to the mothers how to answer the questions (Questionnaire I) provided in English and Bahasa Malaysia. At T0, the questionnaire was given to all participants before the KC-EP was conducted. Each mother had her own identification code number put on the outside of the envelope to match Questionnaire I at T0, T1, and T2 accordingly. The identification numbers started from MEG01(mother experimental group 01).

In addition, signs of readiness to suckle, characterized by moving the tongue and mouth, and the desire for sucking, such as sucking fingers or mother's skin, were observed. As mentioned by Nyqvist (2012), early sucking competence is only observed from 29 weeks postpartum age onward, with the attainment of full breastfeeding as early as 32 weeks postpartum age. Those premature infants born before 32 weeks were given intravenous or nasogastric feeding.

The experimental group, comprised of mother-infant dyads, received a detailed verbal explanation on KC-EP. The contents of the module were verified by health care

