### **3.16.4 Method of Data Collection for Infants**

The researcher recruited the control group of premature infants first and then the experimental group after the nursing intervention program had been completed. The preterm infants in both groups were recruited based on infant admission days and according to mother-infant dyad condition. Firstly, all preterm infants between 28 and 36 + 6 days of gestation (n=48) were recruited by the researchers to participate in the study. The first

recruitment was assigned to the control group. The second recruitment of preterm infants who conformed to the inclusion criteria, i.e. clinically stable and ready to perform KC, was assigned to the experimental group (n=48) after written consent was given by their mothers. Those whose mothers refused to participate were excluded from the study. In the experimental group, data from the preterm infants were collected from the recruitment day until they reached 3 months old. A total of 48 newborn preterm infants from the same setting were given routine care (under servo-controlled radiant warmer or in a cradle with room heaters or blankets) and matched by corrected age. Feeding mode at admission to either group was monitored and jotted down, according to the route of feeding: tube feed, spoon-feed or breastfeeding. Before allocation to a group, it was ensured that the preterm infant was tolerating enteral feeds (over 24 hours) and had no regurgitation at age 28 to 36+6 day weeks of gestation. Corrected age was calculated using the Premature Baby Corrected Age Formula and classified between 28 to 36+6 days weeks of gestation. The baseline weight was calculated from the birth weight and weight on recruitment at T0, and outcome weight gain calculated from the weight on discharge, T1, and T2; this was recorded in the KCPR booklet provided. The body weight of the preterm infant was documented, after removing its clothes, using an electronic weighing scale with an accuracy of 5g at least 2 hours after the last feed and twice a week on Tuesdays and Saturdays according to the hospital protocol for weighing babies. Body weight was measured using a T- scale machine and recorded in grams (g).

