## Part III: Perceived Barriers on KC

**Instruction:** Please indicate a very important perceived barrier of KC. Use the following scale for your responses:

5 = Very Influential

4 = Somewhat Influential

3 = Neither Influential Nor Non-Influential

2 = Not Very Influential

1 = Not Influential at All

No	Statement	5	4	3	2	1
1	Mothers' reluctance to allow KC.					
2	Mothers' belief that technology (e.g., incubators) is more beneficial to premature babies than care a mother can provide.					
3	Mothers' felt no privacy during KC.					
4	Mothers' difficult to assess baby's readiness for KC.					
5	Mothers' reluctance to initiate KC.					
6	Mothers' reluctance to participate in KC.					
7	Mothers' is frequently unavailable to do KC.					
8	Mothers' fear of safety for babies below a certain weight.					
9	Mothers' fear of low temperature during KC.					
10	Mothers' fear of baby's does not breastfeed during KC.					
11	Mothers' feel inability to provide adequate time to other children during KC.					
12	Mothers' belief that KMC is used for babies who are NOT developmentally well.					
13	Mothers' discomfort with exposing their chest during KC.					
14	Mothers' belief that will be much disturbance to the baby during KC.					
15	Mothers' unable to come to visit the baby for a long period of time.					
16	Mothers' felt nursing staff reluctance to participate in KC.					
17	Mothers' feel that KC adds a burden to nurses, inadequate time due to working commitment.					
18	Mothers' felt that KC makes it difficult to nurses to administer care.					
19	Mothers' felt the nursing staff's lack of exposure for mothers participating in KC.					

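### Willingness to perform KC is stated as an entry condition for experimental mothers only, so the two sequential groups may differ in motivation at entry, with an expected but unquantified lean towards the KC-EP

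*Combined protocol and SAP*

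**What the plan says.** The study enrols a control cohort and then, after the nurses have been trained, an experimental cohort in the same NICU. Section 3.3 says that assignment is not random and that "both groups had homogeneous or similar characteristics".

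Entry conditions for mothers appear in several places:

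- **3.7.1 (both groups):** one list covering age, consent, language, no treatment that conflicts with breastfeeding, and ability and eligibility to perform KC. Willingness to perform it is not listed.
- **3.16.1 (control):** "The mothers and premature infants were medically and surgically stable". It continues: "The researchers chose mothers who were ready and returned after 48 hours to meet those who were interested to participate in the study". Selection also required clinical stability and eligibility for KC. Once enrolled, control mothers visited under routine practice and "exercised KC if they were interested".
- **3.16.2 (experimental):** "Both mothers and premature infants were medically and surgically stable, and mothers were willing to perform KC".
- **3.18 (everyone):** willingness to take part in the study.

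On analysis, 3.19.1 plans pretest homogeneity checks, repeated-measures models with interactions, and covariance adjustment for potential confounders. It does not name the T0 score or willingness as a covariate. Willingness is also absent from the mothers' baseline variables (3.8.1, Section A) and from the confounders listed in 3.16.4.

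**The concern.** The stability sentence is nearly the same in the two recruitment sections, but only the experimental one goes on to require willingness to do KC. Read literally, a mother who agrees to be studied but does not want to do KC can be a control and cannot be an experimental participant.

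This matters because there is no randomisation to balance motivation, and because motivation is close to what objective 1 measures: perception of KC and perceived barriers to it. More motivated mothers might also visit and breastfeed more, which could reach the infant outcomes. A difference present at entry could then be read as an effect of the programme.

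**Working it through.** **1. Wording side by side**

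| Condition | Shared list (3.7.1) | Control (3.16.1) | Experimental (3.16.2) |
|---|---|---|---|
| Medically and surgically stable | infant stability only | yes | yes |
| Able or eligible to do KC | yes | yes | yes |
| Interested in the study, consenting | consent | yes, and ready | yes |
| Willing to perform KC | not listed | not stated | stated |

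Only the last row separates the groups. No section applies willingness to perform KC to controls.

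**2. The plan's own figure.** Section 3.7.2 uses a difference of 0.54 and an SD of 0.8: 2 × 7.85 × 0.64 / 0.29 = 34.65, so 35 per group. With the 30% allowance, 35 / (1 − 0.30) = 50. Both reproduce. The final groups are 48 and 48. The point does not depend on this calculation; only the 48 per group is used below.

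**3. How large could the bias be?** The documents give no willingness rate and no difference between willing and unwilling mothers, so both are assumed:

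- q = share of control mothers unwilling to do KC (none in the experimental group)
- d = SDs by which unwilling mothers score worse
- spurious difference with no KC-EP effect = q × d
- standard error = √(2/48) = 0.204 SD
- chance of a significant result favouring the KC-EP = 1 − Φ(1.96 − q·d/0.204); nominal value 2.5%

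If willingness shifts T0 and follow-up equally and T0 is a covariate with correlation r, the standardised shift becomes q·d × (1 − r)/√(1 − r²). At r = 0.5 (assumed) the factor is 0.5/0.866 = 0.577.

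| q | d | Controls affected (q × 48) | q × d (SD) | Unadjusted | T0 as covariate, r = 0.5 |
|---|---|---|---|---|---|
| 0.1 | 0.3 | 4.8 | 0.03 | 3.5% | 3.0% |
| 0.2 | 0.5 | 9.6 | 0.10 | 7.1% | 4.7% |
| 0.3 | 0.8 | 14.4 | 0.24 | 21.6% | 10.0% |
| 0.5 | 1.0 | 24 | 0.50 | 68.8% | 29.3% |

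In the third row, r = 0.3 gives 13.6% and r = 0.7 gives 7.1%. A pure change score, or group-by-time contrast, removes a constant shift altogether: q·d − q·d = 0. It does not remove a shift that grows over time, as it would if willing mothers also learn or change more.

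**4. Which outcomes can be protected.** The mothers' questionnaire is completed at T0 in both groups, and before the KC-EP in the experimental group, so baseline adjustment is available. LOS, a primary outcome in section 3.9, has no T0 value.

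**The case against.** Several arguments on the other side are good.

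- **Controls were also selected.** Section 3.16.1 chose mothers who were ready and interested, and all consented. That narrows the gap. Optional KC describes routine care after enrolment; it shows that controls need not do KC, not that unwilling mothers enrolled.
- **Section 3.16.4 is not a second source.** A reader might set "Firstly, all preterm infants between 28 and 36 + 6 days of gestation (n=48) were recruited by the researchers" against "i.e. clinically stable and ready to perform KC, was assigned to the experimental group (n=48" and see the same asymmetry. The subject of the second sentence is preterm infants who met the inclusion criteria, and the phrase restates those shared criteria. The point therefore rests on the clause in 3.16.2.
- **The barrier items do not record a mother's own reluctance.** A reader might take "Mothers' reluctance to participate in KC" and items 1 and 5 of Appendix E(a), Part III, to mean that entry selects directly on an outcome. The instruction asks how influential each barrier is. These are three of 19 items and only an imperfect proxy for willingness.
- **The T0 data help.** With a constant shift, a group-by-time contrast is unbiased. More favourable T0 scores could also leave less room to improve, so the direction for change scores is not certain.
- **The bias should not be given as a share of the planned effect.** A reader might divide an assumed bias on barriers or perception by 0.54/0.8 = 0.675 SD. That figure is for weight gain, and the plan sets no effect size for the questionnaire scales.

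All of these stand, and they limit size and certainty. They do not supply a willingness condition for controls, a named T0 covariate, or a baseline value for LOS.

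**Conclusion.** The concern holds in limited form. The documents state an entry condition for experimental mothers that they do not state for controls, in a design that relies on the groups being similar. The expected direction is towards the KC-EP. The link is most plausible for perception and perceived barriers, and less certain for breastfeeding, LOS and weight gain.

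The size is unknown. The illustration runs from 0.03 to 0.50 SD, entirely on assumed q and d, and the lower end is negligible. The documents do not support the stronger conclusions that a bias has been shown or that the trial cannot separate selection from effect on the mothers' outcomes. They do show that 3.16.2 and 3.7.1 disagree, and that the plan does not commit to the baseline adjustment that would absorb part of the difference.

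**What to change.** 1. Reconcile 3.16.2 with 3.7.1 so that one entry rule governs both phases. Either drop willingness as a condition, or put the same willingness question to every mother at T0, before any group-specific information, and apply it to both groups.
2. Keep experimental mothers who later decline KC in their group for analysis.
3. Report refusals and their reasons by phase.
4. In 3.19.1, name the T0 score as covariate, or the group-by-time contrast as the test, for each mothers' outcome.

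Section 3.16 describes recruitment in the past tense, with dates in 2018 and 2019. If enrolment is complete, deleting the clause would change nobody's selection and would hide how it was done. In that case, keep the disclosure and use the T0-adjusted analyses. Treat barrier items 1, 5 and 6 only as an imperfect proxy in a sensitivity analysis. They should not be used to restrict the control group: they belong to the outcome scale, and restricting on them invites regression to the mean. State the selection difference as a limitation for LOS and breastfeeding.

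The cost is a little more analysis work and possibly a smaller observed effect. The T0 data are already part of the schedule.

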### **3.16.3 Mothers' Outcome Variables**

Quantitative data on mothers' data were obtained in Phase I and Phase III. The outcome variables were perception, knowledge, perceived barriers in relation to KC, and stress related to admission of preterm infant to the NICU. These variables were assessed three times from T0, T1 to T2. The mothers were instructed to complete Questionnaire I within 10 to 15 minutes without any reference to resources. Firstly, Questionnaire I was delivered at T0; before the KC-EP for mothers started. Next, the mothers were instructed to answer the same structured set of questions in Questionnaire I at T1 and T2 for the post-intervention data. Monitoring the level of personal belief regarding KC at T0, T1 and T2, helps mothers to maintain compliance with KC until their premature infant is 3 months old corrected age. KC, together with breastfeeding, may continue until the infant is 6 months old and breastfeeding combined with solid foods until the infant is 2 years old.

### **3.16.4 Method of Data Collection for Infants**

The researcher recruited the control group of premature infants first and then the experimental group after the nursing intervention program had been completed. The preterm infants in both groups were recruited based on infant admission days and according to mother-infant dyad condition. Firstly, all preterm infants between 28 and 36 + 6 days of gestation (n=48) were recruited by the researchers to participate in the study. The first

recruitment was assigned to the control group. The second recruitment of preterm infants who conformed to the inclusion criteria, i.e. clinically stable and ready to perform KC, was assigned to the experimental group (n=48) after written consent was given by their mothers. Those whose mothers refused to participate were excluded from the study. In the experimental group, data from the preterm infants were collected from the recruitment day until they reached 3 months old. A total of 48 newborn preterm infants from the same setting were given routine care (under servo-controlled radiant warmer or in a cradle with room heaters or blankets) and matched by corrected age. Feeding mode at admission to either group was monitored and jotted down, according to the route of feeding: tube feed, spoon-feed or breastfeeding. Before allocation to a group, it was ensured that the preterm infant was tolerating enteral feeds (over 24 hours) and had no regurgitation at age 28 to 36+6 day weeks of gestation. Corrected age was calculated using the Premature Baby Corrected Age Formula and classified between 28 to 36+6 days weeks of gestation. The baseline weight was calculated from the birth weight and weight on recruitment at T0, and outcome weight gain calculated from the weight on discharge, T1, and T2; this was recorded in the KCPR booklet provided. The body weight of the preterm infant was documented, after removing its clothes, using an electronic weighing scale with an accuracy of 5g at least 2 hours after the last feed and twice a week on Tuesdays and Saturdays according to the hospital protocol for weighing babies. Body weight was measured using a T- scale machine and recorded in grams (g).

After the preterm infants were allocated to the control group or experimental group, they were observed daily, and all observations related to the outcomes of the study were documented in the KCPR booklet i.e. velocity of weight, temperature before, during and after, mode of feeding, type of milk taken and duration of KC provided (in hours/day/week), date of admission and date of discharge in days. In the study by Biswas, Malpani & Ekka, (2016) temperature measurement was taken 10 minutes after KC. However, in this study the

temperature measurement was taken 10 minutes before, 20 to 30 minutes during KC and 10 minutes after the implementation of KC and a regular clinical examination was given in a minimal period of time to avoid hypothermia and cold stress. In the experimental group, duration of KC (in an hour/day) was measured from an accumulated daily 1 hour per day, 4 to 5 hours a week. However, according to Ludington-Hoe, Susan, Morgan, K. & Abouelfetoh (2008), KC is best provided 1 hour a day and 7 days a week until discharge. KC was continued until the premature infant was 3 months old, according to the study requirements. If any problems were detected during KC, they were either rectified or the preterm infant was disqualified from the study. Premature infants were discharged when they showed a good sucking reflex with breast or bottle feeding and had been gaining weight of more than 15g/day to 20g/day for at least three successive days and had achieved a predetermined weight of 1.7kg, in accordance with hospital protocol. On discharge, the nurses routinely advised mothers to come for follow-up until their infant had reached a weight of 2500 grams and to continue breastfeeding. For primary and secondary outcomes, the data from both groups were collected at T0, T1, and T2. The premature infants were followed-up until they were discharged. Conversations and communication between mothers and researchers continued through telephone calls or Whatsapp chat groups accordingly. All related information on KC was shared through the WhatsApp chat group among mothers in the experimental group so that they would remain KC compliant and continue KC at home.

